For Aim 2b, 600 caregivers of patients with ADRD/Delirium (300 control phase; 300 intervention phase) will be surveyed by telephone during (or within one week of) the index hospitalization to assess caregiver-centered outcomes.

Each day PCEs, who will be nurses or social workers on the palliative care team, will approach patients who are currently hospitalized under Aim 1 or Aim 2a. The PCE will then proactively use the goals-of-care video decision aid (or any of the additional videos regarding CPR, hospice, dementia, etc., as relevant and in the appropriate language) to provide educational support and assist in delivering primary palliative care services relating to goals-of-care conversations and ACP documentation. The videos range from 4-6 minutes in length and the PCE will watch the videos together with the patient and caregiver on an iPad (or remotely via telehealth with the caregiver).(130)

The PCE will arrange all video showings to include patient and caregiver (when possible and acceptable to the patient); when patients are unable to view a video (e.g., loss of capacity, delirium), the caregiver will view the video. The videos do not replace clinician counseling; indeed, they are designed to allow the PCE to confirm comprehension and to stimulate

conversation with a shared vocabulary. The PCE will then communicate the patient's or caregiver's wishes to the treating primary medical team to coordinate care.

In cases when the PCE deems that engagement with the full palliative care team is warranted, they will approach the treating primary medical team to place the consult. If/when the PCE exhausts the automated list for patients, they will coordinate with the palliative care consult team to select patients from the list of requested consultations. The PCE role will be fully integrated into existing hospital practices at our sites consistent with the pragmatic nature of this study design.

For Aim 1, the study population will consist of patients 65 years or older who are admitted to one of the study inpatient units in the hospital. For Aim 2a, the study population will consist of any patient ≥ 18 years admitted to one of the study inpatient units in the hospital with a diagnosis of ADRD/Delirium. For Aim 2b, the study population will consist of adult (≥ 18) caregivers of patients identified in Aim 2a. These caregivers will be recruited to complete a phone survey for our secondary caregiver outcomes

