7.1 Subject Inclusion Criteria

Over the two years of the trial, we will examine data on approximately 15,000 patients ≥ 65 admitted to these 23* units for our primary and secondary outcomes (Aim 1). Given the pragmatic nature of this trial, our inclusion criteria are quite broad and consistent with the goal of pragmatic trials.

We will also survey caregivers of 600 patients with ADRD/Delirium to conduct a telephone administered survey for caregiver-centered outcomes (knowledge, confidence, communication satisfaction, decisional satisfaction, and decisional conflict) during the index hospitalization. Caregivers may or may not be designated as ADRD/Delirium legal surrogate decision maker for the patient (i.e., most patients with ADRD/Delirium do not have a legally designated representative.) Any adult identified in the EHR as the contact family member or friend will be eligible to partake in the caregiver survey. Half of surveys will be conducted during the control period; half during the intervention period. Caregivers will be either English- or Spanish-speaking adults, which are the languages in which our surveys are validated. For patients in the control group, surveys will be completed during the hospital stay or within 1 week of discharge. For patients in the intervention group, the survey will be completed AFTER the PCE intervention, and up to 1 week after discharge.

*14 units (7 per hospital) will be included in the stepped wedge trial, an additional 9 units (3 at BMC and 6 at NorthShore) will be used to recruit additional control participants only. These additional units were added due to low recruitment at the start of the study and the decreasing number of control units as the stepped wedge design progresses. The target enrollment of 600 caregivers is still accurate.

Adding delirium to the list of eligible diagnoses will also increase the potential number of eligible subjects. The surveys are applicable to the caregiver of any patient who is not capable of making their own health decisions; this includes patients who are experiencing any sort of memory or cognitive decline.

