7.2 Subject Exclusion Criteria

For Aim 1, there are no exclusion criteria.

For Aim 2a, there are no exclusion criteria.

For Aim 2b, not speaking English or Spanish, which are the languages in which our surveys are validated.

- We will not be including individuals who are not yet adults (infants, children, teenagers)
-
- We will not be including prisoners

8 Study Intervention

A palliative care trained provider (a nurse or social worker on the palliative care team) will serve as the PCE. Using the ACP videos on a tablet via a Video App, the PCE will provide educational support and assist in delivering primary palliative care services relating to in-the-moment goals-of-care conversations and ACP documentation for patients that are hospitalized. PCEs will be members of the Palliative Care team, coordinate daily activities with the team, and report to the head of the Palliative Care service. PCEs will serve in a triage function to manage cases that can be handled with educational support for goals-of-care conversations and ACP documentation or to stimulate full palliative care consultation. PCEs will directly coordinate communication of the patient's preferences with the treating primary medical team. A key aspect of this trial design is the fully integrated role into existing hospital practices of the PCE position.

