PCEs will receive Vital Talk intensive communication skills training via a highly structured series of Zoom conferences. The PCEs will also be trained on use of the ACP certified videos using the ACP App. Training will instruct clinicians on how to: 1. Introduce the videos to patients and caregivers; 2. Use the videos as adjuncts to ACP counseling by clinicians; 3. Select the appropriate video(s) from the entire suite according to patients' needs; and, 4. Prescribe videos for patients and caregivers using the electronic platform. The suite of ACP videos is designed to address common ACP decisions confronting patients at risk or with COVID-19 and their caregivers. The videos also cover all of the decision points surrounding ADRD/Delirium (e.g., feeding tubes, resuscitation, etc.). The videos are intended to be an adjunct to clinician counseling, not to replace it. Suggested videos for clinicians to use with patients will include goals-of-care videos, general ACP videos, intervention-specific videos such as ventilatory support or CPR, and hospice videos. PCEs will also have an array of videos to support caregivers, including videos regarding compassionate extubation if this is relevant.

The PCE will encourage the patient to make their wishes known to their family or other caregiver (and will offer to facilitate a call/video-call) and the attending, and that with the patient's

permission, will relay their wishes to the treating team in addition to completing ACP documentation in the EHR. As an integrated part of existing hospital practice, PCE will communicate with the primary treating team and the palliative care team. When there are palliative care needs beyond ACP (e.g., symptom control) or if the PCE determines that the support of the full palliative care team is warranted, the PCE will recommend to the treating team to place the consult request. The PCE will not be collecting any data for research purposes only. For QI purposes, the Palliative care consult team will keep tracking documents of the PCE activities (number of patients seen per day, amount of time spent with each patient, etc). This is needed for supervisory purposes. These may be reviewed retrospectively by the research team and compared to research data. In this case, an amendment will be submitted to the IRB to cover these activities.

9 Study Procedures

Eligibility

Aim 1 and Aim 2a: Each day, PCEs will review a list of inpatients who are ≥ 65 or have a diagnosis of ADRD/Delirium

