Aim 2b: Study staff will contact identified adult caregivers by phone to describe the survey activity

Recruitment

For Aim 1, all patients over the age of 65 will be included in the trial. For those patients admitted to wards/units in the intervention phase, the PCE will proceed with primary palliative care and view the ACP videos with the patients and family. For patients over the age of 65 admitted to wards/units that are in the control phase, usual care will proceed without the use of the PCE.

For Aim 2a, we will identify 600 inpatients to the study units with ADRD/Delirium who are 18+ years old.

For Aim 2b, 300 caregivers of the patients identified in Aim 2a will be surveyed during the control phase, and 300 caregivers will be surveyed during the intervention phase. For the group of caregivers (N=600) being surveyed for caregiver-centered outcomes, individual verbal informed consent will be obtained. The RA will survey caregivers using a validated survey tool. For patients with ADRD/Delirium and their caregivers that are admitted to a ward/unit that has been randomized to the intervention, the PCE will proceed with the video intervention.

Recruitment efforts for the caregiver survey (Aim 2) will be limited to English- and Spanish-speaking caregivers who are able to independently consent to participate in a research study. Research staff will work with the care team on the inpatient units where identified patients are currently hospitalized. The health care team will locate (either in person or by phone) designated caregivers for identified patients and invite them to participate. A member of the care

team will approach the caregiver and ask if they would be interested in getting a phone call from the research team to get more information about the study. If the caregiver says yes, the RA will call them, read the recruitment script (attached), and, if the subject is willing, review the consent form and complete the survey. If the designated caregiver cannot be located to invite to participate, an invitation letter with opt-out postcard will be mailed to them.

Informed Consent

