We will conduct analyses related to potential effect modification as a step in our model validation process and to identify relationships that can be examined more fully in future research. Should interactions not be found to be statistically significant, we will fit a main effects-only model and use it to formally evaluate confounding by applying a change-in-estimates approach, with a 10% change in estimates being an initial screening criterion. **Secondary outcomes:** Similar procedures will be undertaken to assess intervention effects for the other EHR derived outcomes (documented orders for resuscitation preferences, palliative care consults, hospice enrollment, and documented health care proxies).

For our primary analysis, we will consider our primary outcome (ACP documentation) and our secondary outcomes (resuscitation preferences, palliative care, hospice use, and health care proxies) only for the patient's index hospitalization. However, because we expect some patients to have multiple rehospitalizations during the same step and may also include intervention time (i.e., crossover design), we will perform secondary analyses on all of our primary and secondary outcomes for each patient reviewing all EHR records from the index hospitalization of the patient until their death (or through study period). We will also perform stratified sensitivity analyses of patients who contribute only to control period vs. patients who contribute only to intervention period vs. those that contribute to both control and intervention periods.

We will conduct the above analyses on all Aim 1 and Aim 2a patients for the study primary and secondary outcomes.

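### Aim 2a entry rests on an ADRD/delirium diagnosis with no recording deadline and no stated control-phase identification step, leaving a risk of identification bias that the plan does not address

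*Combined protocol and SAP*

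**What the plan says.** Section 5 defines the Aim 2a population as "any patient ≥ 18 years admitted to one of the study inpatient units in the hospital with a diagnosis of ADRD/Delirium", and the synopsis agrees. Section 7.2 adds "For Aim 2a, there are no exclusion criteria". Neither gives a code list, a data source, a look-back or a cut-off time for the diagnosis. Section 7.1 says of the wider case definition: "Adding delirium to the list of eligible diagnoses will also increase the potential number of eligible subjects".

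Under Eligibility, Section 9 gives one patient-level step for Aims 1 and 2a: "Each day, PCEs will review a list of inpatients who are ≥ 65 or have a diagnosis of ADRD/Delirium". Under Recruitment, for patients over 65 on control-phase units, "usual care will proceed without the use of the PCE". No control-phase identification step is given for Aim 2a. Section 9 (Masking) states that participants and staff are not blinded; its protective measures concern annotation of outcomes.

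Section 12.3 then says: "We will conduct the above analyses on all Aim 1 and Aim 2a patients for the study primary and secondary outcomes". By contrast, the synopsis, Sections 5 and 7.1, and Recruitment in Section 9 define Aim 1 by age.

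**The concern.** In a stepped wedge trial without individual consent, the comparison is protected if each patient's entry to the analysis set cannot depend on the unit's phase. Age meets that condition. An undated diagnosis does not, least of all delirium, which can arise and be charted on any day of the stay. If recognition or charting changes once a unit crosses over, the intervention-phase group contains patients whose control-phase counterparts would never have been flagged. The two groups then differ even if the intervention does nothing.

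The Aim 2a comparison of ACP documentation is the most exposed, followed by the list from which caregivers are drawn. Patients under 65 could also carry the problem into the primary analysis, because the diagnosis is their only way in. Adjustment for calendar time and clustering by unit does not remove a difference in who is counted between phases within the same period.

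**Working it through.** **Step 1: is entry independent of phase?**

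- Age 65 or over (Aim 1): fixed before admission, so yes.
- ADRD/delirium at age 18 or over (Aim 2a): needs a recorded diagnosis with no deadline. Section 5 can be read as meaning a diagnosis present at admission, but nothing fixes that, and the list is reviewed daily.
- Moving between units: Section 12.3 counts a transferred patient's qualifying intervention hours from the time the patient is identified as eligible. For patients under 65 that time depends on the same undated diagnosis, so its timing can also affect phase assignment.

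**Step 2: who is in which set?**

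- Section 7.1 describes about 15,000 patients, all aged 65 or over. Section 9 (NLP Data Collection) gives about the same number for Aims 1 and 2a together. The last sentence on Aim 1 in Section 12.3 covers both aims.
- Section 4.1 and Section 9 (Chart Review) tie the Aim 2a chart review to patients whose caregiver was surveyed. Section 9 (Recruitment) speaks of 600 inpatients. Section 12.3 refers to all Aim 2a patients.

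The plan therefore leaves open whether patients under 65 enter the primary analysis, and whether Aim 2a means every flagged patient or the surveyed 600.

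**Step 3: how large could the shift be?**

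The documents give no recording rates and no figure on this point, so every input here is an assumption except the 25% base rate and the 10-point benchmark, both from Section 12.2. Let the intervention phase flag a fraction g more patients than control, and let p_extra and p_core be the ACP documentation rates of the extra and the core patients when the intervention has no effect.

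Intervention-phase rate = (p_core + g × p_extra) / (1 + g)

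Shift = g / (1 + g) × (p_extra − p_core)

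| g (assumed) | g/(1+g) | 10-point gap | 20-point gap |
|---|---|---|---|
| 0.10 | 0.091 | 0.9 points | 1.8 points |
| 0.20 | 0.167 | 1.7 points | 3.3 points |
| 0.33 | 0.248 | 2.5 points | 5.0 points |

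The sign follows the sign of the gap, so the bias can go either way.

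A second set of assumptions shows how far the answer depends on the inputs. Let the extra patients be a share x = 10% to 30% of the intervention-phase group, with p_extra = 15% to 50% against the 25% base rate. The extremes are 0.30 × (15 − 25) = −3.0 points and 0.30 × (50 − 25) = +7.5 points.

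**Step 4: what reaches the primary result?**

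Multiply by the share of the primary set that is under 65 and enters through Aim 2a. At an assumed 10%, 0.9 to 5.0 points becomes 0.09 to 0.5 points. At an assumed 20%, the wider range becomes 0.20 × (−3.0) = −0.6 to 0.20 × 7.5 = +1.5 points. The benchmark for this outcome is 10 points.

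**The case against.** The strongest reply is that the educators use the list and are not shown to make it. Section 5 calls the list automated. Section 8 says educators collect no data purely for research, and Section 11.5 has research staff and the site investigator extracting the EHR data. Nothing limits the analysis set to patients an educator reviewed. The plan also needs 300 control-phase caregivers, some from the nine control-only units in Section 7.1, so an identification route without educators must exist. All of this stands. A reader might infer from the Eligibility line that educator screening decides who is in Aim 2a; the documents do not support that.

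Two further inferences also fail. The statement that "when patients are unable to view a video (e.g., loss of capacity, delirium), the caregiver will view the video" might suggest that the educator's visit generates delirium diagnoses, but it concerns who watches, and no section says that educators chart delirium. The sentence ending "this includes patients who are experiencing any sort of memory or cognitive decline" might look like a further way into Aim 2a, but it describes the patients whose caregivers the surveys suit.

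There are partial safeguards. Section 12.3 records the numbers approached, screened, ineligible and refusing for Aim 2, and plans balance checks with adjustment. These may reveal a difference between phases and can correct for measured variables, but they do not make entry independent of phase.

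It can also be said that the Section 12.3 sentence means separate analyses of Aim 1 and Aim 2a. That reading is possible, but the text does not say so, and the Aim 2a problem would remain under it.

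**Conclusion.** The point holds as an unaddressed risk. It rests on the open-ended timing of the diagnosis, unblinded staff, and the absence of any stated control-phase identification step. It does not require educators to create the flag.

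The exposure is mainly in the Aim 2a comparison. Its size cannot be known from the documents; 0.9 to 5.0 points follows from assuming 10% to 33% more patients flagged and a 10- to 20-point gap, and other plausible inputs give a wider range in both directions. The 10-point benchmark was set for the primary outcome, so for Aim 2a it is only a yardstick. If Aim 2a means the surveyed 600, caregiver contact and consent also shape the group, and these figures need not carry over.

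The effect on the primary result is small, because entry at age 65 or over is fixed by age, and it disappears if that analysis is limited to those patients.

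**What to change.** 1. In Section 12.3, run the primary analysis on patients aged 65 or over, which matches the Aim 1 definition elsewhere. Report ADRD/delirium patients under 65 only under Aim 2a.
2. For the main Aim 2a analysis, specify one EHR definition (codes and source) applied identically in both phases, all periods and all units, using diagnoses time-stamped before or at study-unit admission. Add a sensitivity analysis that includes diagnoses recorded later in the stay. Report counts of flagged patients by unit and period.
3. Leave the caregiver recruitment list as wide as it is now. Record whether the diagnosis was present at unit admission, and repeat the Aim 2b analysis in that subset. Narrowing the list itself would be a poor trade: three of the seven listed units are ICUs, and Section 7.1 reports low recruitment.
4. Reconcile Section 4.1, Section 9 (Recruitment and Chart Review) and Section 12.3 on who makes up Aim 2a.

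The cost is revised wording, one time-stamped query and one extra data item for surveyed cases. The downside is a smaller main Aim 2a set, since delirium of later onset moves to the sensitivity analysis; the documents give no figure for how much smaller.

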A detailed chart review instrument is attached to the protocol.

Withdrawal

We do not anticipate any circumstances where the caregiver will withdraw from participation in the study. Study staff will make clear to the caregiver that participation is entirely voluntary and may be withdrawn at any time.

Masking

Due to the nature of the intervention, participants and staff will not be blinded to the intervention.

The NLP outcomes adjudication process is not fully automated in this study. We are doing a human-assisted NLP process in which a staff member validates the text presented in the software as a possible outcome. For NLP analysis, the following steps will be taken to ensure blinding to study step assignment by the staff member doing the NLP outcome attribution:

- Prior to adjudication activities, names will be coded
- Annotation will be performed in large batches with all patients enrolled who have clinical notes to that point.
- NLP notes for adjudication will not be grouped by Study ID when presented to annotators. Each note will be annotated individually, without reference to concepts contained in other notes annotated before or after.
- When possible, a staff member who did not enroll the participants will perform the annotation.

Caregiver Surveys

Caregivers will be surveyed using a REDcap survey. The REDCap project will be hosted by BUMC, both sites will enter data into the same project. All subjects will be assigned a unique identifier that will be entered into REDCap. All other PHI will be retained in a linking file that is not shared outside the institution.

Caregiver data will be linked with the associated patient EHR data, but this linking file will be kept locally, and only HIPAA LDS will be shared with other sites included on this protocol.

Costs/Payment

There are no costs to subjects for participating in this study.

Caregivers will be compensated \$50 for completing the survey.

10 Assessment of Safety and Data Safety Monitoring Plan (DSMP)

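### Caregivers reach the Aim 2b survey mainly through an unblinded care team, with no set order of approach and no stated record of non-approaches by phase

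*Combined protocol and SAP*

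**What the plan says.** Section 9 describes entry to the caregiver survey in two places. Under Eligibility, for Aim 2b: "Study staff will contact identified adult caregivers by phone to describe the survey activity". Under Recruitment the process is fuller: "The health care team will locate (either in person or by phone) designated caregivers for identified patients and invite them to participate". A care-team member asks whether the caregiver would accept a call. The research assistant (RA) phones those who agree, reads the script, reviews consent and runs the survey. For a caregiver who cannot be located, "an invitation letter with opt-out postcard will be mailed to them".

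Section 9 (Masking) states: "Due to the nature of the intervention, participants and staff will not be blinded to the intervention". The masking steps that follow concern annotation of clinical notes for the NLP outcomes. None concerns caregiver recruitment or the survey.

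The target is a fixed number per phase: "300 caregivers of the patients identified in Aim 2a will be surveyed during the control phase, and 300 caregivers will be surveyed during the intervention". Section 12.3 plans to count people approached, screened, ineligible and refusing for Aim 2, to compare the groups for balance, and to adjust the Aim 2b models for calendar time and for caregiver characteristics that turn out unbalanced.

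**The concern.** In a stepped wedge trial the units are randomised, but the caregivers are recruited afterwards, when everyone on the unit knows its phase. Randomisation then protects the caregiver comparison only if recruitment works the same way in both phases. Here a clinician who knows the phase decides whom to look for, whom to ask and in what order. The plan sets no rule that limits this choice.

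All five Aim 2b outcomes (knowledge, confidence in future care, communication satisfaction, decisional satisfaction, decisional conflict) plausibly depend on how engaged a caregiver already is with the clinical team. If the mix of engaged and less engaged caregivers differs by phase, part of any difference in scores comes from recruitment and not from the intervention. The Aim 2a manual chart review inherits the same selection, because section 9 limits it to patients whose caregiver completed a survey. The primary outcome is taken from the EHR without consent and is not touched.

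**Working it through.** The plan states no figure on this point, so the check is mainly a comparison of texts.

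**1. Who controls entry.** Read together, the section 9 texts give this sequence: patient identified; care team locates and asks the caregiver; RA calls those who agree. The letter is a second route, but only for caregivers who cannot be located. It does not cover a caregiver whom nobody tries to locate, or one who is located and not asked.

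**2. Where the list comes from.** For Aims 1 and 2a, section 9 (Eligibility) says: "Each day, PCEs will review a list of inpatients who are ≥ 65 or have a diagnosis of ADRD/Delirium". Section 9 (Recruitment) says control units run without the Palliative Care Educator (PCE). The text does not say who draws up the Aim 2a list on control units, or that it is the same list in both phases.

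**3. What the planned counts would show.**
- Listed but never approached: not stated as counted.
- Not located, letter mailed: no separate count stated.
- Approached and declines to the care team: counted as approached and refusing on an ordinary reading, since section 9 uses the word approach for the care team's contact.
- Agrees to a call, then declines to the RA: counted as refusing.
- None of these counts is stated to be reported by phase, unit or entry route.

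**4. What adjustment can reach.** Balance checks and covariate adjustment work on measured characteristics. Among the forms listed in section 11.3, only Sociodemographics is clearly a baseline measure. ACP Engagement is collected in the survey, which in the intervention phase follows the PCE contact (section 7.1), so adjusting for it could remove real effect. Prior engagement with the team is not measured.

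**5. Illustration of size.** The documents give no entry rates and no link between entry and score, so every selection input here is an assumption.

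*Mix of caregivers.* Suppose engaged caregivers score 0.5 to 1.0 SD better, and their share differs between phases by 10 to 20 percentage points (for example 50% against 60% to 70%).
- Spurious difference = difference in share × score gap
- Smallest: 0.10 × 0.5 = 0.05 SD
- Largest: 0.20 × 1.0 = 0.20 SD

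*Entry rates.* Let p be the share of eligible caregivers who enter and ρ the correlation between willingness to enter and score. The mean shift among entrants is ρ·φ(z)/p, with z the (1 − p) normal quantile. This equals 0.497ρ at p = 0.7, 0.798ρ at p = 0.5 and 1.159ρ at p = 0.3.
- 70% control against 50% intervention: (0.798 − 0.497)ρ = 0.301ρ, or 0.03 to 0.15 SD for ρ from 0.1 to 0.5
- 70% against 30%: (1.159 − 0.497)ρ = 0.662ρ, or 0.07 to 0.33 SD
- Equal entry with the same ρ in both phases: 0
- Swapping the phases reverses the sign.

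*Effect on the test.* With 300 per phase (section 9) and the design effect of 2.03 (section 12.2), the effective number per phase is 300/2.03 = 147.8. The standard error is √(2/147.8) = 0.116 SD. For a two-sided 5% normal test with no true effect:

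| Spurious shift (SD) | Type I error |
|---|---|
| 0.05 | 7% |
| 0.10 | 14% |
| 0.15 | 25% |
| 0.20 | 40% |

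**The case against.** The strongest case for the plan has five parts.

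- **The two section 9 texts are compatible.** A reader might infer that the protocol contradicts itself on who makes first contact. The documents do not support that: the Eligibility sentence can be read as a short form of the RA call that follows the care team's question. It leaves out the permission step, which is a wording gap.
- **The PCE is not shown to be the gate.** A reader might infer that PCEs choose the intervention-phase respondents. No text has a PCE inviting caregivers; Recruitment gives the task to the care team in both phases. But PCEs are nurses or social workers integrated into hospital practice (sections 5 and 8), and nothing excludes them from the task.
- **There may be little room to choose.** The documents do not count eligible caregivers. Section 7.1 reports low recruitment, with nine control-only units and the delirium diagnosis added in response. Scarcity limits deliberate picking. It does not remove differences in who is found and who is asked.
- **Safeguards exist.** The letter, the counts, the balance comparison and the adjusted model are real and reduce the risk. They do not reach non-approach or unmeasured engagement. The commitment to CONSORT reporting may lead to counts by phase, but the plan does not say so or say where the flow starts.
- **The clinician's introduction has value.** Replacing it with direct calls could lower response in a trial already short of caregivers, and the RA is unblinded too. This stands, so the introduction should be kept.

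**Conclusion.** The concern holds as a gap in the recruitment procedure for a secondary aim. Entry depends mainly on an unblinded care team acting after the phase is known. No order of approach is stated, and neither is capture of non-approaches or reporting by phase. Selection into the 600 may differ by phase, and the planned adjustment for measured characteristics cannot remove such a difference.

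Direction and size are unknown. A reader might infer that the intervention sample is bound to look better. The documents do not establish that, and the bias could run either way or be absent. The shifts of 0.05 to 0.20 SD and the type I error of 7% to 40% show only that modest selection would matter against a standard error of 0.116 SD. They rest on assumed selection inputs and on the plan's own design effect.

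**What to change.** Keep the permission step and make what precedes it uniform.

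1. Research staff generate the same EHR list of eligible ADRD/delirium inpatients in both phases and pass names to the care team in list order or random order.
2. Any introduction is made by the same non-PCE role in both phases.
3. Log every listed caregiver under one outcome: not approached (with reason), declined to the care team, mailed, declined to the RA, or surveyed.
4. Start the CONSORT flow at the list and report it by phase, unit and entry route.
5. Reword the Aim 2b sentence under Eligibility to match the Recruitment sequence.

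The cost is a protocol amendment and a little more logging by existing research staff. This does not blind anyone. It limits discretion in who is approached and makes any remaining difference between phases visible.
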